### **3.2.4 Missing data and outliers**

#### **3.2.4.1 Missing data**

Missing data will not be imputed. Only observed data will be used in the summaries and analyses.

#### **3.2.4.2 Missing or incomplete dates**

In all listings, missing or incomplete dates should be left as they have been recorded. However, for calculation / sorting / assignation based on dates, the following methods will be used:

The most conservative approach will be systematically considered (i.e. if the onset date of an AE/concomitant medication is missing / incomplete, it is assumed to have occurred during the study treatment phase (i.e. a TEAE for AEs) except if the partial onset date or other data [stop date, ...] indicates differently).

A missing/incomplete date of medical history or disease diagnosis will be assumed to have occurred before any study treatment.

If a partial date and the associated information do not allow to state about the assignation to a group / category, all the possible groups / categories will be considered (i.e.: an AE could be assigned to several possible doses at event onset according to its partial onset date and stop date. Particularly an AE with missing start date will be assigned to each dose received before its end date. Similarly, a medication with partial start and stop dates could be considered as prior and concomitant treatment).

Where this is possible, the derivations based on a partial date will be presented as superior inequalities (i.e.: for an AE started in FEB2004 after the administration performed on 31JAN2004, the days since last dose will be “ $\geq 2$ ”, similarly the duration of ongoing AEs or medication will be “ $\geq xx$ ” according to the start and last visit dates).

#### **3.2.4.3 Outliers**

Any outlier identified prior to database lock, which is impossible/implausible will be excluded from the analysis. For other identified outliers, the impact should be assessed by performing the statistical analysis with the actual values and at least one other analysis eliminating or reducing the outlier effect.

If any outliers are identified after database lock, the statistical analysis should be performed with the actual values and at least one other analysis eliminating or reducing the outlier effect.

A search of outliers by **CCI** [REDACTED] should be performed before database lock and actions with the sponsor should be defined.

### **3.2.5 Subject disposition and withdrawals**

A listing of dates of assessments (relative day) and number of cycles will be presented by subject for each cohort and cancer type.

The numbers and percentages of subjects enrolled and included in each of the ITT, PP and safety populations will be tabulated. The reasons for subject exclusions from each of the populations will be listed and tabulated. In addition, the numbers of subjects who received study

treatment, discontinued and completed at each of the study periods (e.g. active follow-up period, survival follow-up period) will be tabulated. Primary reasons for discontinuation of study treatment will be listed and tabulated.

### ***3.2.6 Demographic and baseline characteristics***

All demographic and baseline characteristics will be listed for the total study population and by cohort, cancer type and subject.

Summary statistics will be provided for demographic and baseline characteristics for the total study population and by cohort.

Demographic characteristics will include

- age (years),
- sex (male, female),
- ethnicity (Hispanic or Latino, Not Hispanic or Latino, not reported),
- race (Asian, American Indian or Alaska Native, Black or African American, Native Hawaiian or Other Pacific Islander, White, not reported, Other),
- country,
- weight (kg),
- height (cm), and
- body mass index (BMI) in kg/m^2,
- body surface area (m^2)
- ECOG Performance Status (0, 1, 2, 3, 4)

Baseline disease characteristics will include

- cancer type (breast cancer, small cell lung cancer)
- time from initial diagnosis of primary disease until the informed consent date (months)
- time from first relapse after last treatment until the informed consent date (months)
- TNM Classification of Malignant Tumours (TNM) Staging for tumour, node, metastasis
  - breast cancer history
    - primary tumour site (left, right)
    - primary tumour histopathological type (invasive carcinoma, carcinoma in situ)
      - Invasive carcinoma (ductal, lobular, not otherwise specified, other)
      - Carcinoma in situ (ductal, not otherwise specified)
    - Scarff-Bloom-Richardson histological grade (SBR I, SBR II, SBR III)
    - Estrogen receptor status (positive, negative, not done)
    - Progesterone receptor status (positive, negative, not done)
    - HER2 receptor status (positive, borderline, negative, not done)
    - BRCA 1 or 2 mutation (positive, negative, not done)
  - small cell lung cancer history
    - anatomical stage - limited disease (0, IA1, IA2, IA3, IB, IIA, IIB, IIIA, IIIB, IIIC)
    - anatomical stage - extensive disease (IVA, IVB)
    - primary tumour site (upper right lobe, middle right lobe, lower right lobe, upper left lobe, lower left lobe, hilar lymph nodes, right bronchus, left bronchus)
  - prior chemotherapy for cancer (yes, no)

- prior hormonal therapy for cancer (yes, no)
- prior immunotherapy for cancer (yes, no)
- prior CDK4/6 inhibitors for breast cancer (yes, no)
- prior targeted agents for cancer (yes, no)
- prior radiotherapy for cancer (yes, no)
- prophylactic cranial irradiation for cancer (yes, no)
- prior surgical procedures for cancer (yes, no)
- Best response from prior chemotherapy, hormonal, immunotherapy, CDK4/6 inhibitors, targeted agents (CR, PR, stable disease (SD), progressive disease (PD), inevaluable (NE), not available (NA))

### **3.2.7 *Medical and surgical history***

Medical and surgical history will be coded initially using MedDRA Version 21.0 and updated regularly.

Listings will present the preferred term and verbatim text. The listings will be sorted by cohort, cancer type, subject, primary system organ class, preferred term and verbatim text.

A frequency table of the number and percentage of subjects will be provided for medical and surgical history by primary system organ class and preferred term for each cohort and cancer type.

### **3.2.8 *Subject compliance***

Number of treatment cycles completed by each subject will also be summarised by cohort and cancer type. Planned Lu-OPS201 dose and planned peptide mass dose will be summarised descriptively by cycle, and by cohort and cancer type and in total.

A listing will be presented for Lu-OPS201 infusion administration (site, side, planned and actual Lu-OPS201 dose, planned and actual peptide mass dose, radioactivity measurement before and after injection, start/end date and time) by subject for each cohort and cancer type. Deviations from planned and actual dose will be presented.

A listing will be presented for Ga-OPS202 administration (actual radioactivity dose, radioactivity dose and volume before and after administration, and date and time) by subject for each cohort and cancer type.

Other information collected on eCRF for Lu-OPS201 and Ga-OPS202 administration will also be listed.

All the protocol deviations identified prior to database lock will be also listed by subject for each cohort and cancer type.

The impact of major protocol deviation on the phase II primary efficacy analysis and phase I and phase II dosimetry analysis will be investigated by comparing the results of the ITT and PP population analyses.

### **3.2.9 *Prior and concomitant therapies***

Prior and concomitant therapies will be coded initially using WHO-Drug Dictionary Version Mar 2018 B3 and updated regularly. The therapeutic class will correspond to the second level of ATC code, which is, corresponding to the first 3 figures of ATC code.

Listings will be presented for the therapeutic class, preferred term and verbatim text. The listings will be sorted by cohort and cancer type, subject, chronological start date, therapeutic class, preferred name and verbatim name.

A frequency table of the number and percentage of subjects will be provided for concomitant therapies by therapeutic class and preferred name for each cohort and cancer type.

Prior, concomitant, and post-treatment medications will be summarised separately. Categorization will be defined as follows:

- Prior medications will include medications which started prior to the start date and time of the first  $^{177}\text{Lu}$ -OPS201 administration.
- Concomitant medications will include medications taken any time from the start date and time of the first  $^{177}\text{Lu}$ -OPS201 administration through 30 days following end date and time of the last  $^{177}\text{Lu}$ -OPS201 administration or until the start of a subsequent anticancer therapy, whichever is earlier. Medications that started prior to the first dose of study drug but continued into treatment are considered concomitant.
- Post-treatment medications will include medications taken any time after from the start date and time of the first  $^{177}\text{Lu}$ -OPS201 administration through 30 days following end of study drug administration or until the start of a subsequent anticancer therapy, whichever is earlier.

Anticancer Treatment received during follow-up period be summarised separately.

### **3.2.10 Pharmacokinetics**

The PK analysis of OPS201 will be performed under the responsibility of the sponsor's Clinical PK department.

Analysis of PK data by a noncompartmental approach will be documented in a separate SAP.

Individual plasma and urine concentrations of OPS201 will be listed and summarised by time points using descriptive statistics for continuous variables (number of available observations, mean, median, standard deviation, minimum, maximum, geometric mean and geometric coefficient of variation assuming lognormally distributed data). Linear and semi-logarithmic plots of individual and mean plasma concentration-time profiles as well as spaghetti plots will be reported.

Any suspicious concentration will be investigated and kept in the PK analysis if possible. All excluded concentrations will be justified in the report.

If OPS201 levels are measurable in plasma and urine, PK parameters of OPS201 (including, but not limited to,  $C_{\max}$ , AUC,  $t_{1/2}$ , Cl,  $V_d$ ,  $A_e$ , renal clearance) will be derived using the noncompartmental approach on the individual plasma concentration-time profiles of OPS201 and on the individual urine concentrations.

An attempt to build an integrated model taking into account PK, dosimetry as well as efficacy and safety data will be made if warranted by the data. The exploratory analysis will be captured in a separate data analysis plan and reported in a standalone report.

### **3.2.11 Radiation Dosimetry of $^{177}\text{Lu}$ -OPS201**

The radiation dosimetry analysis of the radiopharmaceutical  $^{177}\text{Lu}$ -OPS201 will be performed under the responsibility of the sponsor's Clinical PK department.

Further details on dosimetry assessments and on dosimetry parameters will be provided in a separate data analysis plan.

The dosimetry assessments will be performed and reported according to the criteria set by the EANM Dosimetry Committee guidance document: good practice of clinical dosimetry reporting ([Lassmann 2011](#)).

SAP Final: Version 2.0: [03 January 2020]

50/57

Calculations will be conducted on the following parameters (only, but not limited to, in organs showing uptake):

- Maximal uptake (%)
- Organs receiving the highest absorbed dose
- Specific absorbed dose to the target lesion (Gy/GBq)
- Specific absorbed dose per organ (Gy/GBq)
- Cumulative absorbed organ doses (Gy)

Cumulative absorbed organ doses (Gy)/Organs of highest radioactivity uptake will be identified visually. Regions of interest (ROI) will be placed over these organs to determine the relative radioactivity in the respective organs. TACs (time radioactivity curves), describing % IA/ROI of the radioactivity amount injected versus time, considering renal excretion radioactivity) will be derived. The absorbed organ doses of the dose-limiting organs (kidney, BM and liver) will be evaluated and reported to the investigator before the next administration of  $^{177}\text{Lu}$ -OPS201 can be initiated to enable radioactivity adaptations in the event the next dose may exceed the organ limits

for the kidney (23 Gy) and for the BM (1.5 Gy or up to 2 Gy during core trial and additional cycles, respectively). Of note, imaged-based dosimetry results associated to overlying tumors/lesions resulting in absorbed dose overestimation will not be used for dose radioactivity adaptation. In this case, the dose radioactive adaptation will rely on an overall benefit/risk dosimetry evaluation.

A Bayesian power model will be considered to relate the cumulative  $^{177}\text{Lu}$ -OPS201 radioactivity during Cycles 1 and 2 of the dose escalation to the cumulative absorbed dose in the BM and kidney. Vague priors will be used. The posterior predictive distribution of the exposure will be summarised by radioactivity level. Detailed Bayesian power model for phase I dose escalation is documented in a separate analysis plan.

The maximum cumulative absorbed dose where the posterior predictive probability of remaining below the target organ limits (1.5 Gy for BM and 23 Gy for kidney) will be estimated from that model, as the radiation-safety component of the MTCA.

The dosimetry for all organs other than BM and kidney will be assessed and finalised for the final clinical study report, whereas dosimetry data for BM and kidney must be available for the DRB meetings. These data can be reviewed at any time if a major safety issue occurs.

### **3.2.12 *Derived data***

The derived data are variables which are calculated from the raw data in the CRF and not included in the database.

### **3.2.13 *Visit windows***

No study visit windows will be used for analyses. Within CRFs each unscheduled visit will be linked to a scheduled visit which will be used to identify visits.

### **3.2.14 *Rules and data formats***

Data will be presented using an appropriate number of decimal places (i.e. the number of decimal places used does not imply undue precision). Raw data will be presented to the number of decimal places collected, and derived data will be presented to an appropriate number of decimal places. The appropriate number of decimal places will be determined by general practice, mathematical rationale or scientific rationale (e.g. age should be presented in whole numbers).

For summary statistics, the following will be presented n, number of missing values, arithmetic mean, standard deviation, median and the range (minimum, maximum).

Mean, median, standard deviation and standard errors of the mean (SE) values will be reported to one decimal place greater than the raw/derived data that they summarise. Minimum and maximum values will be reported with the same precision as the raw data.

Percentages will be reported to one decimal place and 0% will not be presented. Percentages will be calculated using a denominator of all subjects in a specified population. The denominator will be specified in a footnote to the tables for clarification if necessary.

Lower and upper confidence interval values should be presented to one decimal place more than the raw/derived data (i.e., to the same number of decimal places as the mean).

Percentiles (e.g., 25% or first quartile, 75% third quartile) should be presented to one decimal place more than the raw/derived data.

P-values will be reported to four decimal places (e.g.: p=0.0037), after rounding. P-values which are less than 0.0001 will be presented as '<0.0001'.

All values below or above a limit of detection (e.g. <0.1 or >100) will be listed as such.

All text fields must be left justified and numeric or numeric with some text specification must be decimal justified. Dates will be presented in the format [ddmmmyyyy] and times in the format [hh:mm].

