- Correlation between change (%) in tumour uptake on  $^{68}\text{Ga}$ -OPS202 (assessed based on SUVmax and SUVmean) PET/CT at baseline with tumour response to  $^{177}\text{Lu}$ -OPS201 therapy using ceCT/MRI RECIST v1.1 will be assessed. Spearman correlation coefficient and its p-value will be reported for change (%) in tumour uptake (assessed based on SUVmax and SUVmean) on  $^{68}\text{Ga}$ -OPS202-PET/CT from Screening and tumor response 6 weeks after second  $^{177}\text{Lu}$ -OPS201 administration (second cycle)
- Correlation between the number of lesion counts from  $^{68}\text{Ga}$ -OPS202 in tumour lesions expressing sstr2 on PET/CT images at screening and the number of lesion counts from  $^{177}\text{Lu}$ -OPS201 SPECT/CT at 24 hours after the first  $^{177}\text{Lu}$ -OPS201 administration (Cycle 1) will be assessed by Pearson correlation coefficient and its p-value.
- Proportion of subjects with sstr2-positive tumour lesions by  $^{68}\text{Ga}$ -OPS202 PET/CT scans as assessed by the identification of avid lesions in subjects screened for  $^{177}\text{Lu}$ -OPS201 treatment at baseline will be summarised and analysed in the same manner as ORR.
- Changes in health-related quality of life scores from baseline to EOCT measured by EQ-5D-5L will be summarised descriptively. Frequency tables will be used to display the number and percentage of subjects of reported problems for each level and each dimension of the EQ-5D-5L by scheduled time point. Shift tables presenting the 2-way frequency tabulation from baseline to the worst post-baseline values will be presented for each dimension of the EQ-5D-5L.
- Changes in health-related quality of life scores (global health status/QoL and each functional scale) from baseline to EOCT measured by EORTC QLQ-C30 will be summarised descriptively.

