### 3.2.2.2 *Laboratory data*

Laboratory data must be listed in Standard International (SI) units and also be listed in local units.

A separate listing of normal ranges for SI units will be provided by gender and age where relevant.

Laboratory data will be listed in SI units and abnormal values will be flagged (High, [H], Low [L], clinically significant [C], NCI-CTC grade (G)) where applicable. Any unscheduled laboratory assessments will be flagged [U] in the listings.

A listing will be presented of all values for a subject with at least a clinically significant abnormal value.

Haematological and biochemistry toxicities will be recorded and graded according to the NCI-CTC criteria, version 5.0. The NCI CTC grade (0 to 4) of haematology and biochemistry by cycle and by subject and will be listed in the Section 16.2.8. Listings of the laboratory parameters in section 14.3.4 & 14.3.5 will include listings of NCI-CTC Grade 3 and 4 haematological toxicities, listings of NCI-CTC Grade 3 and 4 biochemical toxicities and listings of out of range biochemistry parameters that could not be graded using NCI-CTC grade (below LLN – normal – above ULN).

For white blood cells (WBC), neutrophils, platelets and haemoglobin, with associated grade 3 or 4 toxicities, nadir and day to nadir will be calculated (refer to Appendix 1, Derived data).

For categorical urinalysis data (normal/abnormal) frequency tables, by cohort and/or cancer type will be presented at each scheduled assessment as well as the change from baseline with the following categories: improved, stable, worsened and abnormal worsening. Shift tables may be presented for the number and percentage of subjects with [normal, abnormal].

For continuous urinalysis data, summary statistics, by -cohort and/or cancer type, will be presented at each scheduled assessment for actual values and changes from baseline.

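### The all-subjects denominator in SAP 3.2.14, combined with observed-only data, makes percentages in tables by scheduled assessment shrink with attrition

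*SAP*

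**What the plan says.** Section 3.2.14 (Rules and data formats) gives a single denominator rule: "Percentages will be calculated using a denominator of all subjects in a specified population". Its only qualifier follows directly: "The denominator will be specified in a footnote to the tables for clarification if necessary".

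Section 3.2.4.1 (Missing data) governs what can be counted: "Missing data will not be imputed. Only observed data will be used in the summaries and analyses".

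Several planned tables are by visit:

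- Section 3.2.1.1, Phase II, plans EQ-5D-5L tables giving the "percentage of subjects of reported problems for each level and each dimension of the EQ-5D-5L by scheduled time point".
- Section 3.2.2.2 (Laboratory data) plans, for categorical urinalysis, "frequency tables, by cohort and/or cancer type will be presented at each scheduled assessment as well as the change from baseline".
- Sections 3.2.2.4 (Vital signs), 3.2.2.5 (ECG) and 3.2.2.6 (Physical examination) plan frequency tables of clinical interpretation at each post-dose assessment. Section 3.2.2.5 adds sinus rhythm at each scheduled assessment.

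None of these sections sets its own denominator or names a row for missing assessments. Section 3.2.14 does ask for n and the number of missing values, but it lists them with the mean, standard deviation, median and range, that is, for continuous summaries.

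**The concern.** The two rules treat an unassessed subject differently. Under 3.2.4.1 the subject contributes no value and cannot be counted in any response category. Under 3.2.14 the same subject is still counted in the denominator. In a table by visit, the percentage in every category then falls as subjects die, withdraw or miss the assessment, even if nothing changes among those still assessed.

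A reader who follows one row across visits, such as severe problems on an EQ-5D-5L dimension or abnormal urinalysis, would see attrition as a decline. A real worsening would be understated and, with enough attrition, could disappear or reverse. The tables at stake support the Phase II quality-of-life and the safety reporting. The primary ORR analysis is not involved.

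**Working it through.** The SAP states no figure on this point, so there is none to reproduce. The check is the arithmetic that follows from its two rules.

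**Inputs**

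- Planned cohort sizes N = 76 (SCLC) and N = 96 (BC), and 10% dropout, from section 1.3.4.
- Attrition of 20%, 30% and 50%: assumptions. The SAP's 10% is a study dropout allowance for sample size; using it as the share unassessed at a visit is also an assumption.
- A prevalence of 40% among those assessed, held constant over visits: an assumption.

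**Formula.** Let n be the number assessed at the visit, N the population size and p the proportion affected among those assessed.

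- Printed under 3.2.14: 100 × (p × n) / N = 100 × p × completion rate, where the completion rate is n / N.
- Among those assessed: 100 × (p × n) / n = 100 × p.

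**A constant 40%**

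| Attrition | n of 76 | Printed, N = 76 | n of 96 | Printed, N = 96 | Among assessed |
|---|---|---|---|---|---|
| 0% | 76 | 40.0% | 96 | 40.0% | 40.0% |
| 10% (SAP figure) | 68 | 35.8% | 86 | 35.8% | 40.0% |
| 20% (assumed) | 61 | 32.1% | 77 | 32.1% | 40.0% |
| 30% (assumed) | 53 | 27.9% | 67 | 27.9% | 40.0% |
| 50% (assumed) | 38 | 20.0% | 48 | 20.0% | 40.0% |

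For example, 0.40 × 68 / 76 = 35.8%. The relative shortfall equals the attrition, apart from rounding n to whole subjects.

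**Rise that would print as flat.** A 40% baseline still prints as 40% when the proportion among those assessed has reached 40 / (1 − attrition):

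- 10% attrition: 40 / 0.9 = 44.4%
- 30% attrition: 40 / 0.7 = 57.1%

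**When a worsening prints as an improvement.** Take an assumed rise from 25% at baseline, with everyone assessed, to 33.3% later among those assessed.

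- The printed value falls below 25% only if completion is below 25 / 33.3 = 75%.
- At 90% completion it is 33.3 × 0.9 = 30.0%: understated, but still a visible worsening.
- At 60 of 96 assessed (62.5% completion) with 20 affected, 20 / 60 = 33.3% prints as 20 / 96 = 20.8%, below a baseline of 24 / 96 = 25.0%. These counts are illustrative and come from no section of the SAP.

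**The case against.** **Section 3.2.14 is a general formatting rule and never mentions visits; 3.2.4.1 can be read as an observed-only denominator.** That reading of 3.2.4.1 is possible. It leaves two sections giving different denominators for the same table, and the explicit one is in 3.2.14. The footnote sentence discloses the denominator and does not change it.

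**Percentages by visit are explicit only for EQ-5D-5L.** This stands. For urinalysis, vital signs, ECG and physical examination the SAP promises frequency tables by assessment. In the urinalysis text, number and percentage attach only to shift tables that are optional. The point reaches those safety tables only so far as percentages are printed in them. Vital signs and ECG do have a not-evaluable category, but nothing assigns unassessed subjects to it.

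**The distortion would be noticed.** Partly true. All categories shrink together, including normal and no problem, so the rows would not sum to 100%. But no missing row or number assessed is required for these tables, and comparing one row across visits still misleads.

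**The quality-of-life endpoint is safe.** This also stands. A reader might infer that the rule can turn a worsening into an improvement in the Phase II quality-of-life endpoint. The SAP does not support that: section 3.1.2 (Subject Reported Outcomes) defines the endpoint as change in scores from baseline to EOCT, and section 3.2.1.1 summarises those changes descriptively. The denominator rule applies to percentages and does not touch them.

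**The study closed early.** Section 5 limits the revised report to listings, and none of the tables discussed here is among them. This reduces the practical effect but does not make the rule sound.

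**Conclusion.** The point holds for percentages in tables by scheduled assessment: explicitly the EQ-5D-5L level percentages, and any percentages in the urinalysis, vital-sign, ECG and physical-examination tables. As written, each equals the percentage among those assessed times the completion rate. A constant 40% prints as about 36% at 10% attrition and about 28% at an assumed 30%.

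A reader might also infer that attrition will routinely make worsening look like improvement. The SAP's own figure does not show that. In the 25% to 33.3% example, reversal needs completion below 75%, whereas at 10% dropout the table would show about 30%. The sizes rest on the assumed prevalences and, beyond 10%, on assumed attrition.

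The effect on the current report is small because section 5 selects listings only. The rule nevertheless remains the SAP's instruction for the planned tables and is worth correcting.

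**What to change.** In section 3.2.14, limit the all-subjects denominator to once-per-subject summaries such as ORR, DCR and any TEAE, where it is appropriate. For tables by scheduled assessment, define the denominator as subjects in the population with a non-missing value at that assessment, and show that n, or a row for missing, beside the population N. This also removes the tension with section 3.2.4.1.

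The cost is one sentence in 3.2.14 and matching table footnotes. It needs no new data and leaves the primary analysis unchanged.
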